5.6 Interruption or discontinuation of treatment

For patients who are unable to tolerate the protocol-specified dosing schedule, dose adjustments are permitted in order to keep the patient on study drug. Toxicity will be assessed using the NIH-NCI Common Terminology Criteria for Adverse Events, version 5.0 (CTCAEv5.0), (http://ctep.cancer.gov/protocolDevelopment/electronic_applications/docs/ctcaev5.pdf). All interruption or changes to study drug administration must be recorded.

5.7 Dose modifications for Elotuzumab

If a Grade 2 or higher infusion reaction occurs during Elotuzumab administration, interrupt the infusion and institute appropriate medical and supportive measures. Upon resolution to Grade 1 or lower, restart EMPLICITI at 0.5 mL per minute and gradually increase at a rate of 0.5 mL per minute every 30 minutes as tolerated to the rate at which the infusion reaction occurred. Resume the escalation regimen if there is no recurrence of the infusion reaction. In patients who experience an infusion reaction, monitor vital signs every 30 minutes for 2 hours after the end of the Elotuzumab infusion. If the infusion reaction recurs, stop the infusion and do not restart on that day. Severe infusion reactions may require permanent discontinuation of Elotuzumab therapy and emergency treatment.

5.8 Dose modifications for lenalidomide-related toxicity

Dose reduction levels for lenalidomide for toxicity management of individual subjects are provided in Table 6:

Table 6 Dose Decrements for Lenalidomide

Nominal Dose (mg)	Reduced Lenalidomide Doses (mg)		
	Dose -1	Dose -2	Dose -3
25	15	10	5
10	5	Discontinue	—

Treatment guidelines for specific hematologic toxicities and nonhematologic toxicities are outlined below. In addition to dose reductions, administration of lenalidomide may be held temporarily in the event of a treatment related toxicity at the investigator's discretion.

If the lenalidomide dose is reduced during a given cycle, the reduced dose level will be continued for the next cycle. If the reduced dose level is tolerated for a complete cycle, the subject may, at the investigator's discretion, resume the dose level prior to the reduction at the start of the subsequent cycle.

Lenalidomide can be discontinued in the event of a treatment-related toxicity that, in the opinion of the investigator, warrants discontinuation. The subject will be considered still on protocol treatment as long as Elotuzumab is being administered.

5.8.1 When platelets	5.8.2 Lenalidomide
5.8.3 Fall to $< 30 \times 10^9 / \text{L}$	5.8.4 Hold dose, hold anticoagulation follow CBC weekly, resume at 1 dose decrement after platelets returned to $> 30 \times 10^9 / \text{L}$
5.8.5 When ANC	
5.8.6 Falls to $< 0.75 \times 10^9 / \text{L}$	Hold dose, administer myeloid growth factor Follow CBC weekly 9 Resume at full dose when $\text{ANC} \geq 0.75 \times 10^9 / \text{L}$
5.8.7 For each subsequent drop to $< 0.75 \times 10^9 / \text{L}$	Hold dose, administer myeloid growth factor Follow CBC weekly 9 Resume at 1 dose decrement when $\text{ANC} \geq 0.75 \times 10^9 / \text{L}$
5.8.8 Any other drug-related nonhematologic toxicity \geq Grade 3	5.8.9 For lenalidomide attribution, hold dose. 5.8.10 Resume at 1 dose decrement when toxicity has resolved to Grade 2 or less or to baseline grade.

5.9 Study drug discontinuation

It will be documented whether or not each patient completed the clinical study. If for any patient either study treatment or observations were discontinued, the reason will be recorded.

Reasons that a patient may discontinue treatment are considered to constitute one of the following:

1. Subject's condition no longer requires study treatment (e.g. satisfactory therapeutic response)
2. Clinical relapse/progression as per the IMWG uniform criteria defined as one or more of the following criteria:
 - a. Development of new soft tissue plasmacytomas or bone lesions (osteoporotic fractures do not constitute progression)
 - b. Definite increase in the size of existing plasmacytomas or bone lesions. A definite increase is defined as a 50% (and ≥ 1 cm) increase as measured serially of the measurable lesion
 - c. Hypercalcemia (> 11 mg/dL);
 - d. Decrease in hemoglobin of ≥ 2 g/dL not related to therapy or other non-myeloma-related conditions;
 - e. Rise in serum creatinine by 2 mg/dL or more from the start of the therapy and attributable to myeloma
 - f. Hyperviscosity related to serum paraprotein
 - g. Adverse event(s)
 - h. Abnormal laboratory value(s)

- i. Abnormal test procedure result(s)
- j. Protocol violation
- k. Subject withdrew consent
- l. Lost to follow-up
- m. Administrative problems
- n. New cancer therapy
- o. Death

5.9.1.1 Follow-up for toxicities

Patients whose treatment is interrupted or permanently discontinued due to an adverse event or abnormal laboratory value must be followed until resolution or stabilization of the event, whichever comes first.

If a patient requires a dose delay of > 21 days from the intended day of the next scheduled dose, then the patient must be discontinued from the study. If however the patient was clearly benefiting from therapy, the patient may be able to continue treatment with either a 5 mg or 10 mg dose reduction at the Investigator discretion, after resolution of the adverse event. All patients will be followed for adverse events and serious adverse events for at least 4 weeks following the last dose of study treatment.

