5.3 Study Treatment Administration

Cycles 1-2

Elotuzumab/lenalidomide will be given in 28-day cycles:

·Elotuzumab will be administered at a dose of 10 mg/kg weekly IV on Days 1, 8, 15, and 22

·Lenalidomide will be administered at a dose of 25(cohort A) or 10 mg (cohort B) once-daily by mouth on Days 1–21

Day	1	8	15	22	28
Elotuzumab	X	X	X	X	
Lenalidomide					

Cycles 3 and beyond**Elotuzumab/lenalidomide will be given in 28-day cycles:**

·Elotuzumab will be administered at a dose of 20 mg/kg monthly IV on Days 1

·Lenalidomide will be administered at a dose of 25(cohort A) or 10 mg (cohort B) once-daily by mouth on Days 1–21

Days	1	8	15	22	28
Elotuzumab		X			Lenalidomide

Based on the emerging data on accelerated infusion, the infusion rate of Elotuzumab will be at 0.5 mL/min for the first 30 minutes, 1 mL/min from 30 to 60 minutes, then 2 mL/min from 60 minutes and beyond on cycle 1 day 1. On cycle 1 day 8, infusion rate will be 3 mL/min for the first 30 minutes, then 4 mL/min from 30 minutes and beyond. Infusion rate will be 5 mL/min from cycle 1 day 15 and after. All patients will receive pre-medication with antihistamine (25 – 50 mg of diphenhydramine PO or IV), H2 blocker (such as ranitidine 50 mg IV or 150 mg PO or equivalent) and acetaminophen (650 – 1000 mg) PO for potential infusion reactions. As part of pre-medication, dexamethasone 28 mg PO will be given between 3 and 24 hours before Elotuzumab and 8 mg IV between 45 and 90 minutes before Elotuzumab as prescribed in the package insert.

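### The dose-delay rule in section 5.9.1.1 is not aligned with Table 6 or section 5.8, and by sending patients off the study it can stop PFS assessment for a toxicity reason

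*Combined protocol and SAP*

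**What the plan says.** Section 5.9.1.1 sets a default and an exception. The default applies once a dose is delayed by more than 21 days: "then the patient must be discontinued from the study". The exception comes in the next sentence. Where there is clear benefit and the adverse event has resolved, "the patient may be able to continue treatment with either a 5 mg or 10 mg dose reduction". The choice is left to the investigator. Neither sentence names a drug, distinguishes the cohorts or mentions Table 6.

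Section 5.8 governs lenalidomide toxicity: "Dose reduction levels for lenalidomide for toxicity management of individual subjects are provided in Table 6". For a nominal 25 mg the levels are 15, 10 and 5 mg. For a nominal 10 mg the row reads "10 5 Discontinue". The tables that follow in 5.8 give resumption rules by type of toxicity: full dose after a first neutrophil fall, one decrement otherwise. They set no time limit on recovery. Section 5.8 also covers a patient whose lenalidomide is stopped for toxicity: "The subject will be considered still on protocol treatment as long as Elotuzumab is being administered".

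The starting doses are in section 5.3: "Lenalidomide will be administered at a dose of 25(cohort A) or 10 mg (cohort B) once-daily by mouth on Days 1–21". Section 6.4 schedules disease assessment at screening, on day 1 of each cycle and at end of treatment. Section 7.1 runs PFS from randomization to death, relapse or progression, or last follow-up.

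**The concern.** Two sections tell the investigator what to do after a toxicity delay, and they do not use the same scale. One works in dose levels specific to each cohort, the other in flat milligram amounts with no stated link to those levels. They also differ on status: one keeps a patient on protocol treatment without lenalidomide, while the other removes a patient from the study for a delay.

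Two things are at stake. Sites may handle the same delay differently, in a trial whose cohorts differ only in lenalidomide dose. And because the wording is about leaving the study rather than stopping treatment, a patient with a long toxicity delay may have no further disease assessment. That patient's PFS would be censored for a reason linked to tolerability, which may itself be linked to prognosis.

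**Working it through.** **Inputs.** Lenalidomide starting doses are 25 mg (cohort A) and 10 mg (cohort B), from section 5.3. The levels are those of Table 6 in section 5.8. The permitted reductions are 5 or 10 mg, from section 5.9.1.1. The plan states no figure to reproduce.

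**Which drug.** Elotuzumab is dosed in mg/kg (sections 5.1 and 5.3), and its modification section (5.7) deals with interrupting, slowing or stopping the infusion, not with a lower dose. Dexamethasone premedication is given in flat milligrams but has no decrements. Lenalidomide is the only study drug with milligram decrements, so I take the exception to mean lenalidomide. That is an inference; the text does not say so.

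**Check.** Current dose minus permitted reduction, compared with the next Table 6 level:

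| Cohort | Current dose (mg) | Minus 5 | Minus 10 | Next in Table 6 |
|---|---|---|---|---|
| A | 25 | 20, not listed | 15, matches | 15 |
| A | 15 | 10, matches | 5, skips a level | 10 |
| A | 10 | 5, matches | 0 | 5 |
| A | 5 | 0 | -5, impossible | none given |
| B | 10 | 5, matches | 0 | 5 |
| B | 5 | 0 | -5, impossible | Discontinue |

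From the two starting doses, two of the four combinations land on the next level (25-10=15; 10-5=5) and two do not (25-5=20; 10-10=0). Over all 12 combinations, 4 land on the next numeric level, 1 skips a level, 1 is unlisted, 4 give zero (one of which coincides with the Discontinue entry in cohort B) and 2 are negative: 4+1+1+4+2=12. A patient on 5 mg has no positive dose under either option.

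**Status of the patient.** Under 5.8, stopping lenalidomide for toxicity while elotuzumab continues leaves the patient on protocol treatment. Under 5.9.1.1, a delay of more than 21 days means "then the patient must be discontinued from the study", unless the exception applies. The delay clock runs from the next scheduled dose without saying of which drug, although one is taken daily on days 1-21 and the other is infused weekly, then every 4 weeks. If a delay of lenalidomide alone counts, a patient delayed 22 days leaves by default, while one who stops the drug altogether stays. Likewise, a first neutrophil fall that takes more than 21 days to recover falls under the full-dose rule in 5.8 and under the leave-or-reduce rule in 5.9.1.1.

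**Effect on PFS.** Section 6.4 has no assessment after end of treatment, and the only follow-up after the last dose that 5.9.1.1 requires concerns adverse events. A patient who leaves for a delay, followed literally, therefore has a last follow-up at or near that point and is censored under 7.1. The plan does not say how many such delays to expect, so the effect on the PFS estimate cannot be computed. For scale only, the final analysis waits for 28 PFS events and the plan does not say whether that is per cohort. If per cohort, 30-28=2 patients can be without an event; if over both cohorts, 60-28=32.

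**The case against.** The best defence is that every numeric step in Table 6 is 5 or 10 mg (25 to 15; 15 to 10; 10 to 5), exactly the two amounts in 5.9.1.1. The sentence can be read as describing whichever step fits the patient's current level, and then neither 20 mg nor 0 mg arises from a starting dose. This is a sensible reading and probably the intended one. But the text does not say it: it offers either amount at the investigator's discretion and does not refer to the table. Nor does it help a patient already on 5 mg.

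Several stronger readings are tempting and should not be drawn:

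- **That 5.9.1.1 contradicts itself.** It does not. It gives a default followed by an explicit exception. The fair criticism is that clear benefit is undefined.
- **That the rule takes cohort B patients to zero, or cannot be applied.** Zero from 10 mg follows only from the larger option, and a reduction to nothing hardly counts as continuing treatment. One option from each starting dose fits Table 6.
- **That 5.8 and 5.9.1.1 flatly conflict on status.** Their triggers differ: lenalidomide stopped for toxicity in one, a long delay in the other. They collide only if a lenalidomide delay alone triggers 5.9.1.1, which is left open.
- **That the plan ends PFS observation when treatment stops.** No section says so, and 5.9 distinguishes stopping treatment from stopping observation. The risk comes from the phrase about leaving the study combined with the absence of any later assessment schedule.

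**Conclusion.** Wrong as written, minor. Read literally, section 5.9.1.1 permits a lenalidomide dose that Table 6 does not list (20 mg) and a reduction to zero where Table 6 gives 5 mg first, and leaves nothing for a patient on 5 mg. Its default of leaving the study does not fit the status rule in 5.8. These conclusions assume that the milligram amounts refer to lenalidomide and, for the status point, that a delay of lenalidomide alone can trigger the rule.

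The statistical consequence is conditional: if sites follow the wording and stop assessing the patient, PFS is censored for a toxicity-related reason. Its size is unknown because the number of long delays is not given. No stated power, alpha or sample-size figure is affected.

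**What to change.** The sponsor must reconcile sections 5.8 (Table 6 and the resumption rules below it) and 5.9.1.1 on three points: which drug the reduction applies to, which drug's delay starts the 21-day clock, and how the milligram amounts relate to the Table 6 levels. The text should separate stopping treatment from leaving the study. It should also state that patients who stop treatment because of a delay continue disease assessment for PFS until progression, death or withdrawal of consent, with a matching entry in section 6.4 and the visit schedule.

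The cost is a protocol wording change and a small amount of extra follow-up using routine laboratory tests. Which dose or discontinuation rule should apply is for the sponsor and the clinical investigators; none is proposed here.

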5.10 Other concomitant medications

Patients must be instructed not to take any additional medications (including over-the-counter products) during the trial without prior consultation with the investigator. All medications taken within 30 days of screening should be recorded. If concomitant therapy must be added or changed, the reason and name of the drug/therapy should be recorded.

In general, the use of any concomitant medication/therapies deemed necessary for the care of the patient are allowed, including drugs given prophylactically (e.g. antiemetics) with the following exceptions:

- No other investigational therapy should be given to patients
- No anticancer agents other than the study medications administered as part of this study protocol should be given to patients. If such agents are required for a patient then the patient must first be withdrawn from the study.
- Leukocyte growth factors (e.g. G-CSF and GM-CSF) are not to be administered systematically but may be prescribed by the investigator for severe neutropenia if this is thought to be appropriate.
- Bisphosphonates are allowed.

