2.2 Secondary Objectives

- Overall response rate (ORR) with Elotuzumab and lenalidomide for each cohort
- Minimum response (MR) or better rate with Elotuzumab and lenalidomide for each cohort
- Time to next treatment (TTNT) for each cohort
- Comparison of clinical outcomes (cohort A versus B)
- Fcγ RIIIA receptor polymorphisms (homozygous for high-affinity V (VV) allele vs. low affinity F (FF) allele)
- Effect of Elotuzumab added to lenalidomide on phenotypic characteristics of the immune infiltrate and correlation with therapeutic efficacy

3 Overall study design

Randomized parallel 2-cohort phase 2 study of Elotuzumab given at 10 mg/kg weekly during induction in combination with lenalidomide (either 25 mg or 10 mg) in patients with multiple myeloma who progress or relapse serologically while on single agent lenalidomide maintenance. Patients will be randomized to either (1) cohort A = lenalidomide 25 mg PO daily days 1-21 or (2) cohort B = lenalidomide 10 mg PO daily days 1-21 with Elotuzumab. We selected the dose of Elotuzumab at 10 mg/kg weekly dosing followed by monthly infusion of 20 mg/kg based on the safety and tolerability profile in the published phase 3 study and other studies of combination therapy with

bortezomib,¹⁻³ as well as an ongoing study in combination with pomalidomide (NCT02612779). Elotuzumab will be administered intravenously on days 1, 8, 15, and 22 during the first 2 cycles, then on day 1 of each cycle starting third cycle. The combination therapy with Elotuzumab and lenalidomide will be continued until further progression of myeloma (based on response criteria) or intolerance.

A total of 60 eligible patients will be randomized into one of two study arms in 1:1 ratio. Stratification factors are risk (standard vs. high) and lenalidomide maintenance post-transplant (yes vs. no). A permuted-block randomization will be applied to ensure a balanced assignment to each treatment arm. Randomization will be accomplished using the Moffitt Cancer Center web-based Subject Registration and Randomization System (SRAR). The SRAR program is accessed using an individual secure identification key that authenticates the user into the Moffitt network.

[figure not shown]
Combination dosing schedule:

(1) Cohort A:

- Elotuzumab 10 mg/kg IV weekly (days 1, 8, 15 and 22) for 2 cycles, then 20 mg/kg every 4 weeks
- Lenalidomide 25 mg PO daily days 1-21 out of a 28-day schedule

(2) Cohort B:

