6. Will only capture in CRF if related to adverse event.
7. All females of childbearing potential should complete a serum pregnancy test within 7 days prior to the administration of Elotuzumab and lenalidomide on day 1 of cycle 1. The pregnancy test should be repeated in week 1 of every cycle (except for cycle 1). Postmenopausal women must have been amenorrheic for ≥ 12 months in order to be considered "of non-childbearing potential".
8. Only grade > 2 adverse events possibly related to study drug will be captured in CRF
9. For patients with urine M spike of less than 200 mg/24 hours at screening, 24-hour urine collection with UPEP will be done every other cycle)

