6.3.1 Adverse events

Information about all adverse events, whether volunteered by the subject, discovered by investigator questioning, or detected through physical examination, laboratory test or other means, will be collected and recorded and followed as appropriate. Adverse events will be collected from cycle 1, day 1, and while the patients are on study treatment only.

An adverse event is the appearance or worsening of any undesirable sign, symptom, or medical condition occurring after starting the study drug even if the event is not considered to be related to study drug. Medical conditions/diseases present before starting study drug are only considered adverse events if they worsen after starting study drug. Abnormal laboratory values or test results constitute adverse events only if they induce clinical signs or symptoms, are considered clinically significant, or require therapy.

The occurrence of adverse events should be sought by non-directive questioning of the patient at each visit during the study. Adverse events also may be detected when they are volunteered by the patient during or between visits or through physical examination, laboratory test, or other assessments. As far as possible, each adverse event should be evaluated to determine:

1. the severity grade (mild, moderate, severe) or (grade 1-4)
2. its relationship to the study drug(s) (suspected/not suspected)
3. its duration (start and end dates or if continuing at final exam)
4. action taken (no action taken; study drug dosage adjusted/temporarily interrupted; study drug permanently discontinued due to this adverse event; concomitant medication taken; non-drug therapy given; hospitalization/prolonged hospitalization)
5. whether it constitutes a serious adverse event (SAE)

All adverse events should be treated appropriately. Such treatment may include changes in study drug treatment including possible interruption or discontinuation, starting or stopping concomitant treatments, changes in the frequency or nature of assessments, hospitalization, or any other medically required intervention. Once an adverse event is detected, it should be followed until its resolution, and assessment should be made at each visit (or more frequently, if necessary) of any changes in severity, the suspected relationship to the study drug, the interventions required to treat it, and the outcome.

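### TTNT is undefined and its event date falls after a required study withdrawal, and no progression or survival follow-up is scheduled once treatment stops

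*Combined protocol and SAP*

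**What the plan says.** The synopsis and sections 2.2 and 7.2 list "Time to next treatment (TTNT) for each cohort" as a secondary endpoint. None gives a start date, an event, a censoring rule or a handling of death. Section 7.2 offers Kaplan-Meier or Gray estimation for time-to-event endpoints in general and does not say which applies to TTNT.

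Section 5.10 bars other anticancer agents and adds: "If such agents are required for a patient then the patient must first be withdrawn from the study". Where concomitant therapy is added, it asks for the drug's name and the reason, not a date. Section 5.9 lists new cancer therapy among the discontinuation reasons and states: "If for any patient either study treatment or observations were discontinued, the reason will be recorded".

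Patients can stop before progression. Section 5.9 lists "Subject's condition no longer requires study treatment (e.g. satisfactory therapeutic response") as well as adverse events and withdrawn consent. Section 5.9.1.1 says of a dose delay over 21 days: "then the patient must be discontinued from the study", with an exception for a patient who is clearly benefiting.

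Section 6.4 schedules disease assessment on Day 1 of each cycle and at end of treatment. Table 6-1 closes with an End of Study column and has no row for survival or next therapy. After the last dose the plan provides only for safety: "All patients will be followed for adverse events and serious adverse events for at least 4 weeks following the last dose of study treatment" (5.9.1.1), and SAE reporting for 30 days after dosing stops (9.4.2).

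Section 7.1 runs PFS from randomisation to death, relapse/progression or the last follow-up date, which it does not define. Section 6.2 accepts laboratory progression only on two consecutive assessments before any new therapy.

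**The concern.** Under the plan's own withdrawal rule and visit schedule, one of its secondary endpoints is not captured. The TTNT event can happen only once the patient has left the study, so the date could be rebuilt only later, from charts, and without a definition to rebuild it to.

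The primary endpoint is exposed less widely. A patient who stops event-free has no planned observation of the events that 7.1 counts, apart from the end-of-treatment assessment and the safety window. Each cohort is judged against a fixed 7-month median. If exit is related to prognosis, no control arm shares the resulting bias. Section 7.1 also has no rule for new therapy begun before progression, so that choice would be made with the data in hand.

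**Working it through.** **1. Tracing the TTNT date.** The event is the start of a new anticancer agent. Section 5.10 puts withdrawal before that start. Section 5.9 records a reason, and 5.10 a name and a reason. Table 6-1 and 6.4 schedule nothing after End of Study or end of treatment. No scheduled item holds the date.

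**2. Tracing PFS after event-free exit.** The last scheduled disease assessment is at end of treatment. A death within 30 days of dosing would be reported, because death is an SAE (9.2) and SAEs run to 30 days (9.4.2). Nothing later is scheduled. The 12 months of follow-up in section 7 is an input to the power calculation, not a visit plan.

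**3. Reproducing the stated 85%.** Inputs from section 7: 30 patients per cohort, median 7 v 12 months, one-sided alpha 0.05, accrual 24 months, follow-up 12 months. Hazards are ln2/7 = 0.0990 and ln2/12 = 0.0578 per month.

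- Probability of an event by month 36 with uniform accrual: 1 − (e^(−12λ) − e^(−36λ))/(24λ).
- Expected events: 26.5 (null), 21.9 (alternative).
- Power = Φ[(ln(12/7) − 1.645/√26.5) × √21.9] = Φ[(0.539 − 0.320) × 4.68] = 0.848.

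A simulated one-sample log-rank test gives 85.2% with variance (O+E)/2 and 82.4% with variance E. All of these assume that no patient exits event-free.

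**4. Exit unrelated to prognosis.** Assumptions: lifetime probability q of exit before progression; exit hazard λq/(1−q); censoring at exit; one-sample log-rank test; analysis at month 36; true median 12 months. Expected events are 30(1−q) × [1 − (e^(−12t) − e^(−36t))/(24t)], with t = λ/(1−q).

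| q | exits by month 36 | events | power, V=(O+E)/2 | power, V=E |
|---|---|---|---|---|
| 0 | 0 | 21.9 | 85% | 82% |
| 10% | 2.3 | 20.6 | 84% | 81% |
| 20% | 4.8 | 19.2 | 82% | 78% |
| 30% | 7.5 | 17.6 | 79% | 75% |

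If the 10/20/30% is instead read as exit by month 12, the formula in step 3 gives 83/80/78%.

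**5. Exit linked to prognosis.** Let L be the on-treatment progression hazard, g = Lq/(1−q) the exit hazard, and h = ln2/m the post-exit hazard. True PFS is S(t) = e^(−(L+g)t) + [g/(L+g−h)] × [e^(−ht) − e^(−(L+g)t)]. Solve S(7) = 0.5 for L. With censoring at exit, the Kaplan-Meier median tends to ln2/L.

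- Post-exit median m = 3.5 months: 7.2/7.5/7.9 for q = 10/20/30% (at 30%, L = 0.0882).
- Post-exit median m = 12 months: 6.9/6.7/6.5 (at 30%, L = 0.1068).

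**The case against.** Treatment is meant to run to progression (sections 3, 5.1, 5.2), so event-free exits may be few, and with unchanged prognosis the loss of power is modest. Both points stand, and they limit the PFS part. They do not touch TTNT, which is affected for every patient who starts another therapy.

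Stronger readings are tempting but are not supported:

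- **That the plan censors PFS at treatment exit by rule.** Section 7.1 names only an undefined last follow-up date. Section 5.9 distinguishes stopping treatment from stopping observations. Censoring at exit is what happens in practice because nothing later is scheduled.
- **That the 21-day rule ends all observation.** Its exception speaks of continuing treatment, so the study there may mean study treatment.
- **That no death after exit is seen.** Deaths within 30 days of dosing are reportable.
- **That every enrolled patient has a next-treatment date that goes missing.** Patients still on treatment, or who die without further therapy, have no such date.
- **That the bias favours the regimen.** Section 5.9 lists exits of opposite kinds, satisfactory response and adverse events, so the direction is unknown.
- **That power collapses.** A figure near 65% needs 30% of patients to exit, all with a 24-month post-exit median. Its only textual support is one generic item in 5.9.

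**Conclusion.** The point holds and should be fixed. For TTNT it rests on the text alone: the endpoint is named, undefined, and placed after a required withdrawal with no date collected. For PFS, progression after event-free exit, and death beyond the safety window, have no scheduled ascertainment, and new therapy before progression has no rule.

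The PFS figures are illustrative: about 85% power falling to 84/82/79%, and a true 7-month median reading as about 6.5 to 7.9 months at 30% exit. They depend on assumed exit rates and post-exit prognosis, on a one-sample log-rank test that the plan does not name (7.1 gives only Kaplan-Meier and a Brookmeyer-Crowley interval), and on analysis at month 36, whereas section 7 triggers the analysis at 28 PFS events. Confidence is high for the TTNT gap and lower for the size of any PFS effect.

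**What to change.** 1. In 5.10 and 5.9.1.1, separate stopping study treatment from leaving the study. Leave the treatment-stopping rules as they are.
2. Add a post-treatment follow-up column to Table 6-1, about every 3 months, drawn from routine-care records with no mandated tests. Record progression, start date of the next anti-myeloma treatment, and vital status.
3. Define TTNT as randomisation to start of the next anti-myeloma treatment, with a stated rule for death (for example a competing event, using the Gray and Fine-Gray methods already in 7.2). Censor others at last contact.
4. In 7.1, count progression or death after stopping treatment as PFS events. Prespecify censoring at the last assessment before new therapy, which agrees with 6.2, and one sensitivity analysis that counts later events. Report event-free exits with reasons by cohort.

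If half of exiting patients start new therapy at once and stay censored, power in step 4 becomes about 84/84/82% instead of 84/82/79%. This assumes unchanged prognosis and exact capture of later events.

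The cost is protocol wording and chart abstraction for up to about 60 patients. Off-treatment progression dates will be coarser, and some routine-care progressions may lack the confirmation 6.2 requires. Patients who withdraw consent stay unobserved, and some informative censoring at new therapy remains, which only the sensitivity analysis can show.
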